- h: The Months 3, 6, 9, 12, 15, 18, 21, 24, 27, 30, and 33 ECHO may be performed any time within 3 weeks prior to the study visit. If a subject discontinues early from the study, the ECHO should be scheduled as soon as practical (see Table 7).
- i: Females of child-bearing potential
- j: For subjects enrolling from one of the core studies, use data collected at Visit 12 of ZX008-1501 or ZX008-1502 for Visit 1 unless clinical laboratory evaluation is warranted based on significant changes in subject status. Visit 2 clinical laboratory evaluation is optional based on subject status for all cohorts.
- k: Months 6, 15, and 27 only.
- l: Visits 3 and 4 (Months 1 and 2) only.
- m: Only adverse events related to cardiac safety will be collected at this visit (see Table 7).
- n: Not to be completed for de novo subjects >18 years old.

Table 5. Schedule of Assessments for Subjects from Core Study ZX008-1504

Study Assessments	OLE Treatment Period				Post-Dosing	Cardiac Follow-up	
	Visit 1 ^a	Visit 2 ^b		Visits 3-15 (Months 1, 2, 3, 6, 9, 12, 15, 18, 21, 24, 27, 30, and 33)			Visit 16 ^c (EOS/ET) Month 36
Study Day	1 ^a	15		30, 60, 90, 180, 270, 365, 455, 545, 635, 725, 815, 905, 995	1085	1099	3 and 6 months post last dose
		Clinic	Phone				
Informed Consent	X						
Entry Criteria	X						
Demographics	X						
Medical/Neurological History	X ^a						
Epilepsy History	X ^a						
Physical Examination, complete	X ^a				X		X ^d
Physical Examination, abbreviated		X		X			X ^d
Neurological Examination, complete	X ^c				X		
Neurological Examination, abbreviated		X		X			
Vital signs	X	X		X	X		
Weight, Height, BMI	X ^a	X		X	X		
12-lead ECG	X ^a			X	X		X ^d
Doppler ECHO	X ^a			X ^{f,g}	X		X ^d
Urine Pregnancy Test ^h	X			X	X		
Clinical laboratory evaluation (hematology/clinical chemistry/urinalysis, etc)	X ⁱ	X ⁱ		X	X		
Urine THC Panel/Whole blood CBD	X ^a			X	X		
Plasma sample for background AEDs		X		X	X		
Tanner Staging (for subjects > 7 years old)	X ^a			X ^j	X		X ^j
C-SSRS	X ^a			X	X		
CGI-I (assessed by parent/caregiver)	X ^a			X	X		
CGI-I (assessed by principal investigator)	X ^a			X	X		
QOLCE	X ^a			X	X		
EQ-5D-5L (QoL of parent/caregiver)	X ^a			X	X		
BRIEF	X ^a			X	X		
Healthcare utilization questions	X ^a			X	X		

continued

Table 5. Schedule of Assessments for Subjects from Core Study ZX008-1504 (continued)

Study Assessments	OLE Treatment Period				Post-Dosing	Cardiac Follow-up	

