5.2 SAFETY (SAF) POPULATION

The SAF population is the set of all enrolled subjects who received at least one dose of ZX008 during the open label extension. Safety analyses will be performed on the SAF Population.

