6.4 SAFETY ANALYSIS

Safety will be assessed through evaluation of AEs, Laboratory data (hematology, chemistry, urinalysis), vital signs (blood pressure, heart rate, temperature, and respiratory rate), Physical examination, Neurological examination, 12-lead ECGs, Doppler ECHOs, Tanner Staging, BRIEF to measure cognition, and Columbia–Suicide Severity Rating Scale.

All safety analyses will be performed for the SAF population and will be reported for all subjects overall. Select analyses may be repeated by treatment group, for example, treatment-emergent adverse events initiating on or before Visit 2 (Week 2), Visit 3 (Month 1), and Visit 4 (Month 2).

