The original terms used by the investigators in the eCRFs to identify AEs will be coded using the most recent version of the MedDRA implemented by the sponsor at the end of the study.

6.4.1.1 Overview of Adverse Events:

The number and percent of patients with at least one of the following events will be summarized in an overall summary table:

- TEAE
- Serious TEAE
- Related TEAE
- Related serious TEAE
- Severe TEAEs
- Adverse events of special interest
- Deaths

The percentage denominator for the calculation of percentage will be the number of subjects in the SAF population. The above summary will be provided for the OLE treatment period.

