6.4.11 Brief Rating Inventory of Executive Function (BRIEF, BRIEF-P, BRIEF-A)

The Behavior Rating Inventory of Executive Function (BRIEF™), preschool version, BRIEF-P, and adult version (used for subjects aged 19-35), are standardized, validated rating scales to measure executive function in children within the home and school environments that will be assessed by the parent according to the schedule in Table 1.

The BRIEF measures multiple aspects of executive functioning; scales include Inhibit, Shift, Emotional Control, Initiate, Working Memory, Plan/Organize, Organization of Materials and Monitor.

The original BRIEF was the basis for the development of the BRIEF-P. The BRIEF-P Rating Form consists of 63 items that measure various aspects of executive functioning: Inhibit Shift, Emotional Control, Working Memory, and Plan/Organize.

The BRIEF-A Rating Form consists of 75 items that measure various aspects of executive functioning. Nine overlapping scales are created in two different indexes. For the BRIEF-A, the BRI is composed of four scales: Inhibit, Shift, Emotional Control, and Self-Monitor. The Metacognition Index is composed of five scales: Initiate, Working Memory, Plan/Organize, Task Monitor, and Organization of Materials. The BRI and MI combine to yield the GEC Index.

For the BRIEF, BRIEF-P, and BRIEF-A, mean scores at Baseline, End of Study/ET and mean change from baseline to End of Study/ET, and descriptive statistics will be presented by treatment group and overall for the Safety population (SAF).

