Name of Treatment Group	Treatment Group Code	Description	AED Treatment from Feeder study	Feeder Study(s)	Approximate n
PBO-ZX008 OL	1	Placebo arms in all studies	Placebo in feeder study along with any protocol-approved background AED combination; no active ZX008	1501, 1502, 1504 Cohort 2	120
ZX 0.2 – ZX008 OL	2	0.2 arm in DB Studies	Any protocol-approved background AED combination; plus, ZX008 0.2 mg/kg/day max 30 mg	1501, 1502	80
ZX 0.8 – ZX008 OL	3	0.8 arm in DB studies	Any protocol-approved background AED combination; plus, ZX008 0.8 mg/kg/day max 30 mg	1501, 1502	80
ZX 0.5 – ZX008 OL	4	Active arm in 1504 cohort 2	Protocol-approved background regimen including STP + VPA + CBZ; plus ZX008 0.5 mg/kg/day max 20 mg	1504 Cohort 2	40
PK – ZX008 OL	5	Cohort 1 PK Study - Open label study		1504 Cohort 1	40
Summary Treatment Groups¹					
ZX DBA – ZX008 OL	6 (Groups2-4)	All Active arms in the DB studies	Any protocol-approved background regimen, plus ZX008 at any protocol-approved dose – DB Studies only	1501, 1502, 1504 Cohort 2	200
ZX DB – ZX008 OL	7 (Groups1-4)	All subjects in randomized double-blind (DB) studies	Any protocol-approved background regimen at any protocol-approved dose – DB Studies only		
ZX – ZX008 OL	8 (Groups2-5)	All Active arms	Any protocol-approved background regimen, plus ZX008 at any protocol-approved dose – All studies	1501, 1502, 1504 Cohort 1, 1504 Cohort 2	240
ZX008 OL	9 (Groups1-5)	All Subjects in 1503 excluding de novo subjects	Any protocol-approved background regimen at any protocol-approved dose – All studies	1501, 1502, 1504 (both cohorts)	360
De Novo Subjects	10		Subjects entering 1503 who had not participated in any of the core studies	None	35

Notes:1: Subjects in 1504 cohort 1 do not have a pre-study treatment baseline for seizures and are not included in analyses requiring baseline (Core) seizure frequency.

Analysis Summary types

Type	Treatment By Groups (Codes as above)
A	1, 2, 3, 4,5,9, 10
B	1, 8, 9, 10
C	1, 6, 7, 10

TLF Shells

Zogenix International Limited
ZX008-1503

NOTES:

The TFL shells provided are for the final study report. For the interim analysis, please note the following:

Programming Prioritization for Interim Analysis, 2018

Provide summaries for ZX008 OL (Group 9), i.e., "All Subjects" column only

- 1 = High priority -
- 2 = Medium Priority
- 3 = Low Priority

LIST OF TABLES, FIGURES AND LISTINGS FOR FINAL REPORT

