Treatment-Emergent Adverse Events by MedDRA System Organ Class and Preferred Term
Safety Population (Japan)

Table 14.3.1.2.1.1
Treatment-Emergent Adverse Events during Open-label Treatment Periods by Age Group (<6 yrs, ≥6 yrs), MedDRA System Organ Class and Preferred Term
Safety Population

Programming note: Similar to Table SADS21 in ISS, but population is 1503 Safety, and only use AEs occurring during 1503. One column only, ALL subjects in ZX008 OL. Alternatively, this is just the above Table, 14.3.1.2.1, by Age Group.

Programming Note: Use the shell for 14.3.1.2.1.1 to produce same format for 14.3.1.2.1.4.

Table 14.3.1.2.1.4
Treatment-Emergent Adverse Events during Open-label Treatment Periods by Age Group (<6 yrs, ≥6 yrs), MedDRA System Organ Class and Preferred Term
Safety Population (Japan)

Table 14.3.1.2.1.2
Treatment-emergent Adverse Events with Decreased Appetite or Hypophagia during Open-Label Treatment Period
Safety Population

	Placebo (N = xxx)	ZX008 0.2 mg (N = XXX)	ZX008 0.5 mg (N = XXX)	ZX008 0.8 mg (N = XXX)	ZX008 OL (N = XXX)	De Novo Subjects (N = XXX)
Decreased Appetite	XX (XX.X%)	XX (XX.X%)	XX (XX.X%)	XX (XX.X%)	XX (XX.X%)	XX (XX.X%)
Had adverse event unresolved	XX (XX.X%)	XX (XX.X%)	XX (XX.X%)	XX (XX.X%)	XX (XX.X%)	XX (XX.X%)
Duration of event for subjects who had event resolved	XX (XX.X%)	XX (XX.X%)	XX (XX.X%)	XX (XX.X%)	XX (XX.X%)	XX (XX.X%)
n	XX	XX	XX	XX	XX	XX
Mean	XX.X	XX.X	XX.X	XX.X	XX.X	XX.X
SD	XX.XX	XX.XX	XX.XX	XX.XX	XX.XX	XX.XX
Median	XX	XX	XX	XX	XX	XX
Min, Max	XX	XX	XX	XX	XX	XX
Hypophagia	XX (XX.X%)	XX (XX.X%)	XX (XX.X%)	XX (XX.X%)	XX (XX.X%)	XX (XX.X%)
Had adverse event unresolved	XX (XX.X%)	XX (XX.X%)	XX (XX.X%)	XX (XX.X%)	XX (XX.X%)	XX (XX.X%)
Duration of event for subjects who had event resolved	XX (XX.X%)	XX (XX.X%)	XX (XX.X%)	XX (XX.X%)	XX (XX.X%)	XX (XX.X%)
n	XX	XX	XX	XX	XX	XX
Mean	XX.X	XX.X	XX.X	XX.X	XX.X	XX.X
SD	XX.XX	XX.XX	XX.XX	XX.XX	XX.XX	XX.XX
Median	XX	XX	XX	XX	XX	XX
Min, Max	XX	XX	XX	XX	XX	XX

TEAE = Treatment-Emergent Adverse Event.

Note: Events considered are all TEAEs occurring during OLE. Adverse events are classified as treatment-emergent if they started on or after the date of first dose of study treatment. Adverse events with partial or missing start dates are classified as treatment-emergent, unless the non-missing components of the start date confirm otherwise.

Programmin note: Please see annotations in ISS for SST16

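### The overall safety column in the final-report shells leaves out de novo subjects, so it does not cover the Safety population the SAP defines, and the Tanner and BRIEF summary tables have no de novo column

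*SAP*

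**What the plan says.** **Text of the SAP**

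- Section 5.2: "The SAF population is the set of all enrolled subjects who received at least one dose of ZX008 during the open label extension". De novo subjects are not excepted.
- Section 6.4: "All safety analyses will be performed for the SAF population and will be reported for all subjects overall".
- Section 6.4.1.1, on the adverse-event overview: "The percentage denominator for the calculation of percentage will be the number of subjects in the SAF population".
- Section 6.4.11 asks for BRIEF, BRIEF-P and BRIEF-A by treatment group and overall for the Safety population.

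**TLF shells**

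- The treatment-groups table describes Group 9 (ZX008 OL, Groups 1-5) as "All Subjects in 1503 excluding de novo subjects". The general programming notes call Group 9 the all-subjects column. De novo subjects are Group 10, with an approximate n of 35.
- Summary types A, B and C each list Group 10 on its own. None has a total of Groups 1-5 plus 10.
- Tables 14.3.1.1 (overview), 14.3.1.2.1 (SOC and preferred term), 14.3.1.6 (severity), 14.3.4.1 (laboratory) and 14.4.5.1 (C-SSRS) show Group 9 beside a de novo column, under a Safety Population title.
- The Tanner shell (boys, reused for girls) and Table 14.4.6.1 (BRIEF-P, reused for BRIEF in 14.4.6.2) have only Groups 1-5 and 9.
- Table 14.4.1.3 (weight by age) excludes de novo subjects. Table 14.4.1.4 gives their weight, but not by age.
- The note to Table 14.3.1.2.1.1 (TEAEs by age) first says "One column only, ALL subjects in ZX008 OL", then offers Table 14.3.1.2.1 by age group as an alternative.

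**The concern.** Long-term safety is the primary objective, and two parts of the same document give different meanings to the overall safety result. A programmer following the shells would produce a column presented as all subjects under a Safety Population title, whose denominator is smaller than the Safety population of section 5.2. Even the Study Populations table (14.1.1.3) has no total column, so no column there prints the full Safety population N.

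The subjects left out differ from the rest. They have no feeder-study exposure and were not selected by completing a feeder study. Section 1 also describes entrants aged over 18 to 35. An event confined to them would not change the overall rate.

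For Tanner staging, BRIEF-P and BRIEF the gap is wider. Table 4 schedules Tanner staging and BRIEF for de novo subjects, and the plan allows for some who are children. Section 6.1.3 defines age strata from 2 to 18 years using age at core-study entry or at de novo entry. The PedsQL footnote to Table 4 bars only the older ones: "Not to be completed for de novo subjects >18 years old". For such subjects these assessments would be collected but not summarised.

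**Working it through.** **1. Reproduce the plan's Group 9 counts.** Group 9 is Groups 1-5.

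- TLF treatment-groups table: 120 + 80 + 80 + 40 + 40 = 360, as stated.
- Section 3.2, Table 1: 120 + 80 + 80 + 40 + 18 = 338, as stated.

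The two differ only in Group 5 (40 against 18). Both totals are reached without any de novo subjects, which confirms what the column contains.

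**2. Size of the omission.** The de novo count is 35 in the shells; Table 1 leaves it to be determined. I apply 35 to both Group 9 counts.

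| Group 9 | Groups 1-5 plus 10 | De novo share |
|---|---|---|
| 338 | 373 | 35/373 = 9.4% |
| 360 | 395 | 35/395 = 8.9% |

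**3. Effect on a common event (assumed rates).** Suppose 20% of Group 9 and between 10% and 40% of de novo subjects have the event. Pooled rate = (n9 × 0.20 + 35 × d) / (n9 + 35).

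- n9 = 338: (67.6 + 3.5)/373 = 19.1% to (67.6 + 14)/373 = 21.9%
- n9 = 360: (72 + 3.5)/395 = 19.1% to (72 + 14)/395 = 21.8%

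The column as planned would read 20.0%, so the shift is at most about two percentage points.

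**4. Effect on a rare event (hypothetical).** Two cases, both de novo:

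- Group 9 column: 0/338, exact two-sided 95% upper limit 1.1%
- Pooled column: 2/373 = 0.5%, upper limit 1.9%
- De novo column: 2/35 = 5.7%

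The event is visible in the de novo column but absent from the overall one.

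**5. Effect at the 5% threshold (hypothetical).** An event in 16 of 338 is 4.7% and would not be listed if Group 9 drives the cut. With 5 more cases among de novo subjects, 21/373 = 5.6% would be listed.

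**6. Which safety summaries lack de novo data.**

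| Output | De novo in a summary table? |
|---|---|
| AE overview, SOC/PT, severity, laboratory, C-SSRS | Yes, own column; no pooled total |
| Tanner (boys, girls), BRIEF-P, BRIEF | No; listings only |
| Weight by age | No; weight over time shown separately, not by age |
| TEAEs by age | Unclear; the note gives two alternatives, and only 14.3.1.2.1 by age has a de novo column |
| 14.3.1.9.1 and 14.3.1.10.1 (feeder-study periods) | No, and rightly so |

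**The case against.** The strongest reply is that little is hidden. The de novo group is openly labelled and has its own column in most safety shells. Deaths and SAEs are listed individually, and Listing 16.2.7.3 is dedicated to de novo adverse events. In step 4 above, 2/35 is more conspicuous than 2/373. Subjects with and without feeder exposure also differ, so keeping them apart is sensible, and one sentence redefining overall in section 6.4 would remove the contradiction. This stands as a limit on the harm. It does not reconcile sections 5.2, 6.4 and 6.4.1.1 with the shells, and it does not supply the missing Tanner and BRIEF columns.

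A reader might also infer more than the SAP supports:

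- *No safety output covers the full Safety population.* Figure 14.4.1.2 is programmed on the safety flag with no de novo exclusion. Exposure by sex (14.1.5.1.2), the dose and exposure tables 14.1.5.1.7.1 to 14.1.5.1.10.1, and the any-dose column of 14.3.1.10.2 do not say either way. They are ambiguous, not proven exclusions.
- *TEAEs by age omit de novo subjects.* Only one of the two alternatives in that note does so.
- *The 5% cut is fixed on Group 9.* The footnote tying it to the all-subjects column is introduced for the interim. Section 6.4.1.2 names no column for the final report.
- *Roll-over subjects who turn 19 lose their BRIEF-A data.* The summary table is limited to de novo subjects, while section 6.4.11 describes the "adult version (used for subjects aged 19-35" without that limit. The SAP does not say that a roll-over subject changes instrument at 19, and the BRIEF-A listings carry no de novo restriction.
- *De novo Tanner and BRIEF data are lost.* Listings 16.2.9.3.1 to 16.2.9.3.4 and 16.2.9.4 are not restricted, so the data would be listed. How many de novo subjects are children is not stated.

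**Conclusion.** The contradiction is real and affects the final report. The overall column in the adverse-event, laboratory and C-SSRS shells omits about 9% of the Safety population as section 5.2 defines it. This figure rests on the planning counts: 35 de novo subjects and a Group 9 of 338 or 360.

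The Tanner (boys and girls), BRIEF-P and BRIEF summaries have no place for de novo subjects, although the assessments are scheduled for them. The practical size of that gap depends on how many enrol at 18 or under. Weight by age also leaves them out, and TEAEs by age is unresolved.

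The expected distortion of common-event rates is small. The reason to act is that the headline safety result should match its stated population and denominator, particularly for rare events and near the 5% threshold. The separate column and the listings reduce the risk that an event would be missed altogether.

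**What to change.** 1. Add a column for all ZX008-1503 subjects (Groups 1-5 plus 10) to the Safety-population tables for the extension period, and state in section 6.4 that it is the overall result. Keep Groups 9 and 10 as separate columns.
2. Add a de novo column to the Tanner tables for boys and girls and to Tables 14.4.6.1 (BRIEF-P) and 14.4.6.2 (BRIEF).
3. Resolve the note to Table 14.3.1.2.1.1 in favour of Table 14.3.1.2.1 by age group, which carries the de novo column. Treat weight by age (14.4.1.3) in the same way as the other extension-period tables.
4. State that the pooled column drives the 5% cut in the final report.
5. Leave the feeder-period tables 14.3.1.9.1 and 14.3.1.10.1 as they are.

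The cost is one or two columns per table. The pooled column mixes subjects with and without feeder-study exposure, but the retained separate columns show that split. If the sponsor prefers no pooled column, the minimum is to say in sections 6.4 and 6.4.1.1 that overall means core-study subjects only; item 2 would still be needed.
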